
A subject who meets any of the following criteria will be **excluded** from participation in this study:

1. Positive urine pregnancy test at screening.
2. Any medical disease or condition that, in the opinion of the site Principal Investigator (PI) or appropriate sub-investigator, precludes study participation.
3. Presence of self-reported or medically documented uncontrolled significant medical or psychiatric condition(s) other than COVID-19.
4. Reports a recent positive test result (within the past 6 months) for hepatitis B surface antigen, hepatitis C virus antibody, or HIV-1 antibodies at screening.

5. Has a history of alcohol abuse or other recreational drug (excluding cannabis) use within 1 month of Study Day 1.
6. COVID-19 signs associated with acute respiratory distress or imminent serious medical outcomes.^{^^}
7. BMI ≥ 36 .
8. **Subjects living (e.g., siblings, spouses, relatives, roommates) in the same household cannot be enrolled.**
9. Has participated in another investigational study involving any intervention for SARS-CoV-2/COVID- 19 within the past 6 months or any clinical trial with interventional investigational product within 30 days of screening.
10. Currently enrolled in or plans to participate in another clinical trial with an interventional investigational agent that will be received during the study period.
11. History of hospitalization within the past 60 days.
12. History of systemic antiviral therapies within the past 30 days.
13. History of oral corticoid steroid use within the past 14 days or steroid injection within the past 6 months. Active use of nasal or inhalable steroids is also exclusionary. Topical steroids are not exclusionary.
14. Has a history of hypersensitivity or severe allergic reaction (e.g., anaphylaxis, generalized urticaria, angioedema, other significant reaction) to nitrates, nitrates or sun exposure.
15. Has any oral abnormality (e.g. ulcer, oral mucositis, gingivitis) that in the opinion of the investigator would interfere with device use, or intra-oral metal body piercings that cannot be removed for the duration of the study. Metal orthodontia is permitted as braces will be covered by the device mouthpiece.

^{^^}Potential Study Subjects Presenting with any of the following should be referred for immediate medical care and are not eligible for the study

- Fever $> 104^{\circ}$ F
- Cough with sputum production
- Rales and/or rhonchi

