4.2 Study Schedule of Activities

Study Procedures	Follow-up Period (Visit Window)				
	1	2	3	5 (-1 to +1)	8/ET (-1 to +1)
Study Days					
Informed Consent	X				
COVID19 Screening & SARS-CoV-2 Rapid Antigen Test***	X				
Medical History & Physical Examination	X	Changes since last visit only	Changes since last visit only	Changes since last visit only	X
Oropharyngeal Assessment	X*	Changes since last visit only	Changes since last visit only	Changes since last visit only	X
Urine Pregnancy Test	X				X
Concomitant Medication History/New	Baseline	Changes since last visit only			
Comprehensive Metabolic Panel & CBC	X				X
Vital Signs	X				X
Methemoglobin	X				X
Adverse Event Assessment / Reactogenicity	Baseline	X	X	X	X
Demographics, Inclusion / Exclusion Review	X				
Diary Dispensation/Collection	X				X
Treatment at Site	X**	X**	X**		
Biospecimen collection for viral assays (3 specimens)****	X		X	X	X
COVID-19 Severity Score	X				X
Collect RD-X19 Device	NA			Cohort 1	Cohort 2

*On Day 1 to be evaluated 30 minutes after first illumination at site.

**Only one treatment will be done on site, other treatment will be done at home, i.e. if afternoon appointment, subject will complete morning treatment at home and afternoon treatment administered at the site. For scheduling purposes, recommended interval between treatment is approximately 8 – 12 hours but not \leq 4 hours.

***Subjects presenting at the time of screening that have tested positive via a SARS-CoV-2 rapid antigen test at or within the past 24 hours of the screening visit and can provide documentation confirming proper identification, the date of the test and testing location, positivity of the result, and name/identity of the assay used to generate the result, are also eligible for enrollment and the rapid antigen test does not have to be repeated at the site.

**** At Baseline and days 3, 5, and 8, subjects will provide two saliva specimens and an oropharyngeal swab for virology endpoint assessments. One saliva specimen will be collected, preserved, and shipped fresh to a central lab for assessment of SARS-CoV-2 mRNA via RT-qPCR. The second specimen and the oropharyngeal swab will be collected in separate collection tubes, frozen, and stored at the site and shipped to a central lab at the end of each cohort.

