- Review all pre-study medications, vitamins, supplements, and therapies up to 14 days prior to the start of screening that could impact the use of, or response to, the device and record on the appropriate e-CRF. Subjects are allowed to use over-the-counter medications and remedies to alleviate symptoms (e.g. acetaminophen, ibuprofen, cough drops, etc. and should be recorded.)
- Measure vital signs (HR, BP, **RR**, and oral temperature) and height and weight for determination of BMI.
- Perform full physical examination which will include assessments of the following organs and organ systems: skin, head, ears, eyes, nose, and throat (HEENT), neck, lungs, heart, liver, spleen, abdomen, extremities, lymph nodes (axillary and cervical), and nervous system.
- Obtain blood and urine for clinical screening laboratory evaluations:
 - Comprehensive Metabolic Panel (fasting or non-fasting)
 - CBC with differential
 - Urine pregnancy test (in women of childbearing potential)
- Review inclusion and exclusion criteria.

The overall eligibility of the subject to participate in the study will be assessed once all screening values are available. The screening process can be suspended prior to complete assessment at any time if exclusions are identified by the study team.

Study subjects who qualify for inclusion will be immediately randomized for their day 1 visit.

If a physiologic parameter, e.g., vital signs, is outside of the protocol-specified range, then the measurement may be repeated once if, in the judgment of the participating clinical site PI or appropriate sub-investigator, the abnormality is the result of an acute, short-term, rapidly reversible condition (e.g., stress, anxiety or “white coat syndrome”) or other source of error. A physiologic parameter may also be repeated if there is a technical problem with the measurement caused by malfunctioning, or an inappropriate measuring device (i.e., inappropriate-sized BP cuff).

A subject may be re-screened if there is a transient disease status (e.g., absent signs and symptoms associated with mild COVID-19), or if a protocol eligibility criterion that is not met at the initial time of screening, will be met by rescreening of all assessments within the next 2 days using the same subject number.

No subjects may be screened more than twice due to a screening failure result as defined above.

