 - Subjects will be observed in the clinic for at least 30 minutes post the first RD-X19 illumination. The oropharynx and surrounding tissues will be examined. Reactogenicity assessments will be performed on Days 1, 2, 3, 5, and 8. An oropharyngeal examination will also be performed on Days 1 and 8 and during unscheduled visits and early termination visits and recorded on the appropriate source document prior to discharge from the clinic. Interim or unscheduled oropharyngeal examinations will be performed, if necessary, to evaluate AEs.
- Vital signs:

Vital sign measurements will include systolic and diastolic BP, HR, **RR**, and oral temperature. Vital signs will be measured at timepoints specified in protocol section 4.2. Subjects must not eat or drink anything hot or cold within 10 minutes prior to taking their oral temperature or using the RD-X19 device.
- Clinical laboratory evaluations:
 - Fasting is not required before collection of clinical laboratory evaluations.

- Urine pregnancy test will be performed locally by the site laboratory at the screening visit and at the final study visit. Results must be confirmed as negative prior to randomization on Day 1 and allocation and use of the RD-X19 device.
- Clinical laboratory evaluations CMP and CBC (diff) will be performed locally by the site selected laboratories.
 - Clinical safety laboratory evaluations will be performed locally by the site laboratory.
 - Blood and urine will be collected at timepoints specified in the protocol section 4.2.

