5.1 Methodological Considerations

General Conventions

SAS software (version 9.4 or higher) will be used for all data analyses and tabulations.

The study is not powered for hypothesis testing. P-values will be considered descriptive and will not be adjusted for multiplicity.

Data for all investigational centers will be pooled for analysis.

Unless specified elsewhere, baseline is defined as the last available measurement prior to administration of study drug. Change from baseline will be calculated as the post-baseline value minus the baseline value.

Summary tables will include the data based upon the protocol scheduled time points. For subjects who are early discontinued from the study, all efficacy assessments captured at the ET visit will be assigned to the nearest protocol scheduled time point.

Visit of Treatment Period	Range*	Target Day
Visit 1 / Baseline (Day 1)	Study Day = 1	Day 1
Visit 2 / Day 2	Study Day = 2	Day 2
Visit 3 / Day 3	Study Day = 3	Day 3
Visit 4 / Day 5 (± 1 day)	Study Day 4 to 6	Day 5
Visit 5 / Day 8 (± 1 day)	Study Day 7 to 9	Day 8

*Study day = date of visit - date of first treatment + 1

Descriptive statistics of continuous variables will include n, mean, standard deviation (SD), median, minimum and maximum. Generally, the minimum and maximum values will be presented to the same decimal precision as the raw values, the mean and median values to one more, and the SD, to two more decimal places than the raw values. Summaries for categorical data will include frequencies and percentages. Percentages will be presented to one decimal place.

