Counts reflect numbers of subjects reporting one or more TEAE that map to the MedDRA system organ class/preferred term. At each level of summarization (system organ class or preferred term), subjects reporting more than one TEAE are counted only once under the earliest Study Day when the event of greatest severity was reported.

Source: Listing 16.2.7

O:\Studies\EmitBio\EB-P12-01\Biometrics\Programs\Tables\xxx.sas ran on Month Day, Year at hh:mm on data from Month Day, Year.

Table 14.3.2 – Reactogenicity by Visit for Safety Population

Study Visit	Category	4 Days RD-X19 n (%)	7 Days RD-X19 n (%)	Sham n (%)
Visit 1 /Day 1	N	XX	XX	XX
	n (%) subject with illumination site pain	XX (XX.X)	XX (XX.X)	XX (XX.X)
	n (%) subject with illumination site erythema	XX (XX.X)	XX (XX.X)	XX (XX.X)
	n (%) subject with illumination site Edema/Induration	XX (XX.X)	XX (XX.X)	XX (XX.X)
	n (%) subject with other pain, redness, swelling, or lesion of the oral mucosa	XX (XX.X)	XX (XX.X)	XX (XX.X)
Visit 2 /Day 2	N	XX	XX	XX
	n (%) subject with illumination site pain	XX (XX.X)	XX (XX.X)	XX (XX.X)
	n (%) subject with illumination site erythema	XX (XX.X)	XX (XX.X)	XX (XX.X)
	n (%) subject with illumination site Edema/Induration	XX (XX.X)	XX (XX.X)	XX (XX.X)
	n (%) subject with other pain, redness, swelling, or lesion of the oral mucosa	XX (XX.X)	XX (XX.X)	XX (XX.X)
Visit 3 /Day 3	...			
Visit 4 /Day 5	...			
Visit 5 /Day 8/ET	...			

Source: Listing 16.2.9.1

O:\Studies\EmitBio\EB-P12-01\Biometrics\Programs\Tables\xxx.sas ran on Month Day, Year at hh:mm on data from Month Day, Year.

Table 14.3.3 – Oropharyngeal Assessment by Visit for Safety Population

Study Visit	Category	4 Days RD-X19 n (%)	7 Days RD-X19 n (%)	Sham n (%)
Overall*	N	XX	XX	XX
	Normal	XX (XX.X)	XX (XX.X)	XX (XX.X)
	Abnormal	XX (XX.X)	XX (XX.X)	XX (XX.X)
Visit 1 /Day 1	N	XX	XX	XX
	Normal	XX (XX.X)	XX (XX.X)	XX (XX.X)
	Abnormal	XX (XX.X)	XX (XX.X)	XX (XX.X)
Visit 2 /Day 2	N	XX	XX	XX
	Normal	XX (XX.X)	XX (XX.X)	XX (XX.X)
	Abnormal	XX (XX.X)	XX (XX.X)	XX (XX.X)
Visit 3 /Day 3	...			
Visit 4 /Day 5	...			
Visit 5 /Day 8/ET	...			

*For Overall, Normal category includes subjects with a normal result for all visits; Abnormal category includes subjects with an abnormal result at any visit.

Source: Listing 16.2.9.2

O:\Studies\EmitBio\EB-P12-01\Biometrics\Programs\Tables\xxx.sas ran on Month Day, Year at hh:mm on data from Month Day, Year.

Table 14.3.4 – Vital Signs by Visit for Safety Population

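### The dedicated oropharyngeal assessment has no pre-illumination time point, so Table 14.3.3 mixes throat findings present at entry with new ones and dilutes the contrast with sham

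*Combined protocol and SAP*

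**What the plan says.** **Timing.** In the protocol schedule (Section 4.2) and the SAP schedule (Section 7.1), the Day 1 cell of the oropharyngeal row carries the footnote "On Day 1 to be evaluated 30 minutes after first illumination at site". Days 2, 3 and 5 are limited to changes since the preceding visit, and Day 8 is a full assessment. Protocol Section 9.2 agrees: "Subjects will be observed in the clinic for at least 30 minutes post the first RD-X19 illumination", after which the oropharynx is examined. It adds that "An oropharyngeal examination will also be performed on Days 1 and 8 and during unscheduled visits and early termination visits", and does not place the Day 1 examination before illumination.

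**What is examined before treatment.** The full physical examination at screening (Section 9.1.1) includes the throat. The last exclusion criterion (number 15 in protocol version 2.0) applies to a subject who "Has any oral abnormality (e.g. ulcer, oral mucositis, gingivitis) that in the opinion of the investigator would interfere with device use". In the schedule row "Adverse Event Assessment / Reactogenicity", the Day 1 cell reads Baseline.

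**Tabulation.** SAP Section 5.1 states that, unless specified elsewhere, "baseline is defined as the last available measurement prior to administration of study drug". Table 14.3.3 reports Normal or Abnormal by visit and overall. For the overall row, "Abnormal category includes subjects with an abnormal result at any visit". Its Day 1 row is not labelled as baseline and it shows no change, whereas Tables 14.3.4 (vital signs) and 14.3.5 (methemoglobin) do both. Table 14.3.3 and Listing 16.2.9.2 are among the interim outputs after Cohort 1. The physical examination listing (16.2.9.4) is not.

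**The concern.** The oropharynx is the tissue that the device illuminates, and local site reaction was one of the three adverse event terms reported in the Phase I study. That study enrolled healthy volunteers. This trial enrols people with symptomatic infection for whom sore throat counts towards eligibility, and the oral exclusion removes only abnormality that the investigator thinks would interfere with device use. Some subjects can therefore be expected to have an abnormal throat before they are treated.

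The planned oropharyngeal record cannot show which ones. Its first entry comes after the first exposure, and the entries on Days 2, 3 and 5 are changes relative to an examination that was itself made after exposure. A reviewer of Table 14.3.3, at the interim or at the end, sees entry findings and new findings in a single count. At stake are the clarity of one local-safety table reviewed before Cohort 2 opens and the ability to say, for an individual subject, whether a finding arose after illumination.

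**Working it through.** The documents state no figure for this table, so there is none to reproduce. The check has two parts.

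**1. Tracing the pre-treatment throat record**

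| Record | Before first illumination? | Reaches Table 14.3.3 or Listing 16.2.9.2? |
|---|---|---|
| Oropharyngeal assessment, Day 1 | No, 30 minutes after | Yes |
| Oropharyngeal assessment, Days 2, 3, 5 | No, changes only | Yes |
| Screening physical examination (throat) | Yes | No, goes to Listing 16.2.9.4 |
| Oral-abnormality eligibility check | Yes | No, goes to Listing 16.2.2.2 |
| Day 1 adverse event / reactogenicity entry | Labelled Baseline | No; solicited events come from direct questioning (Section 9.2.2) and are shown in Table 14.3.2 |

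A pre-treatment look at the throat therefore exists, but it is not linked to the oropharyngeal tabulation. The reactogenicity entry does not fill the gap. Table 14.3.2 counts illumination-site reactions, which cannot precede illumination, and its Day 1 row is not labelled as baseline.

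**2. Size of the dilution (illustration)**

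Inputs from the documents: nominal allocation of 20 device to 10 sham per cohort (protocol Section 6.1).

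Assumed inputs, which the documents do not give:
- b, the share with an abnormal throat at entry, equal in both arms: 30%, 40% and 60%.
- d, the share of device subjects with a new reaction, independent of b: 20%.
- No new throat findings on sham.
- Entry abnormality is still recorded at one or more study visits.
- A reaction in an already abnormal throat can be recorded as a worsening.

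Under the any-visit rule:
- device rate = b + (1 − b)d
- sham rate = b
- visible excess = (1 − b)d

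| b | Device | Sham | Visible excess |
|---|---|---|---|
| 30% | 0.30 + 0.70 × 0.20 = 44% | 30% | 14 points |
| 40% | 0.40 + 0.60 × 0.20 = 52% | 40% | 12 points |
| 60% | 0.60 + 0.40 × 0.20 = 68% | 60% | 8 points |

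With new-or-worsened findings tabulated, the contrast is 20% v 0%, an excess of 20 points. The shrinkage factor is 1 − b whatever the value of d. With d = 30%, for example, an excess of 30 points becomes 24, 18 and 12 at b = 20%, 40% and 60%.

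**What this means for 20 v 10 subjects.** Treat the two arms as independent binomials with the rates above. Ask how often the observed device proportion does not exceed the sham proportion.
- New-or-worsened tabulation: this happens only if no device subject reacts, 0.80^20 = 0.012, about 1%.
- Any-visit tabulation: 26%, 31% and 39% at b = 30%, 40% and 60%.

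**Formal testing.** The expected counts without dilution, 4/20 v 0/10, give a two-sided Fisher p of 0.27. Power of the two-sided 5% Fisher test at 20 v 10 is at most about 7% in all of these scenarios. The loss is therefore in descriptive reading.

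**The case against.** The strongest reply is that the throat is not unexamined before treatment and that the trial has a concurrent sham arm. Both points stand, and they limit what can be said. A reader might draw five stronger conclusions that the documents do not support.

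- **That there is no pre-treatment throat examination.** There is one at screening, together with the eligibility check. Subjects also score sore throat from 0 to 3 at screening, and protocol Section 9.2.1 treats conditions present at screening as baseline rather than as adverse events. The gap is the missing link to one table and its listing.
- **That this is the main local-safety examination.** The protocol does not call it that, and Table 1 does not list it. Solicited reactogenicity is a separate local measure with its own table, also reviewed at the interim. Neither the pausing criteria nor the protocol's specific interim safety criteria use normal or abnormal oropharyngeal status.
- **That an acute Day 1 reaction disappears into the reference.** It does not. Table 14.3.3 has its own Day 1 row, the overall row counts that visit, and Listing 16.2.9.2 gives the result and a description as well as the change.
- **That a device effect cannot be separated from COVID-19 at all.** Randomization to sham under double-blind conditions leaves entry findings balanced in expectation, so the between-arm comparison keeps its direction.
- **That the SAP breaches its own baseline definition.** Table 14.3.3 computes no change from baseline and does not label Day 1 as one.

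The magnitude is also open to challenge. The rates are assumptions, and zero new findings on sham is optimistic, because Clarification Memorandum 1 says that further COVID-19 signs and symptoms may emerge after screening. The 20 v 10 comparison applies to the interim; the final tables show one pooled sham column, nominally 20 v 20. None of this restores the missing distinction between entry and new findings in Table 14.3.3.

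**Conclusion.** The point holds in a limited form. The dedicated oropharyngeal assessment has no pre-illumination value, and the pre-treatment throat records that do exist are not carried into Table 14.3.3 or Listing 16.2.9.2. Because infected throats can be enrolled, the any-visit count combines entry findings with new ones. The consequence is a diluted descriptive contrast and no within-subject attribution in that table, at the interim and at the end. It is not a directional bias.

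Under the stated assumptions the visible excess falls from 20 points to between 14 and 8, and at the interim the chance of seeing no excess rises from about 1% to between 26% and 39%. These figures depend on the assumed 20% reaction rate, the 30% to 60% entry abnormality and the absence of new sham findings. The proportional loss depends mainly on the entry rate.

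A reader might infer that a difference which would otherwise have been demonstrated is being lost. That does not follow: even the undiluted expected counts give p = 0.27, and SAP Section 5.1 says that the study is not powered for hypothesis testing. The change is still worth making, because a descriptive table is useful only if its categories mean what the reader takes them to mean.

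**What to change.** 1. Enter the pre-illumination oropharyngeal status on the oropharyngeal form, with a description of any abnormality, using the examination already done at screening on Day 1. Name this entry in the SAP as the baseline for the assessment.
2. Keep the 30-minute examination and label it as the first post-treatment value. Amend the footnote in both schedules so that the two Day 1 entries are distinct.
3. Add rows to Table 14.3.3, by visit and overall, for findings that are new or worsened relative to the pre-illumination entry. The existing Normal and Abnormal rows can stay. Carry the pre-illumination entry into Listing 16.2.9.2, so that it reaches the interim review.
4. Reconcile the Day 1 Baseline entry for reactogenicity with Section 9.2, which schedules a Day 1 reactogenicity assessment, and with the Day 1 row of Table 14.3.2, so that it is clear which value precedes illumination.

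The cost is one form entry per subject, taken from an examination already performed, and a table-shell change with the matching listing field. No additional visit or procedure is needed.

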5 INTRODUCTION

5.1 Background and Study Rationale

In December 2019 the Wuhan Municipal Health Committee identified an outbreak of viral pneumonia cases of unknown cause. Coronavirus ribonucleic acid (RNA) was quickly identified in some of these patients. As of October 11, 2020 there were approximately 37 million confirmed cases worldwide (>7.7 million in the US) and over 1,075,000 deaths (~215,000 in the US). The only FDA approved intervention currently is Remdesivir for hospitalized subjects with COVID-19. Other interventions currently being used are through the Emergency Use Authorizations (EUA), against SARS-CoV-2 / COVID-19. Social distancing and personal protective equipment constitute our only viable countermeasures to help reduce incidence of community acquisition and transmission of SARS-CoV-2. Vaccine candidates are being developed at an unprecedented speed, however their efficacy and safety is unknown and will not be fully defined for many months. Remdesivir, Convalescent Immune Plasma and SoluMedrol are all used to treat patients hospitalized with COVID-19, but none has received marketing approval as a therapeutic for uncomplicated COVID-19. Therefore, there remains an urgent public health need for rapid development of novel measures for prevention and treatment of SARS-CoV-2 and COVID-19.

RD-X19 through both direct and intermediate mechanisms, kills cell-free virus by as much as 99.99% and inhibits cell-associated replication of SARS-CoV-2 by 99.9% when measured at 24 hours after a single 5 minute treatment. Putative key virucidal mechanisms include upregulation of nitric oxide in epithelial tissue through increase of nitric oxide synthases (NOSs) and stimulation of the instantaneous release of the body's bound store of nitric oxide. Nitric oxide produced physiologically in epithelial tissues also induces and attracts effector cells of the innate immune system, including natural killer (NK) cells, neutrophils and macrophages to phagocytize virus-infected cells at the site of primary infection. The technology utilized by RD-X19 has been repeatedly demonstrated to provide high-level viral control in multiple, consistent, expert-laboratory *in vitro* studies. The mechanism of action, utilizing augmented innate immunity, presents an unprecedented opportunity for protection that is not specific antigen-directed or dependent.

